2 INTRODUCTION

2.1 STUDY RATIONALE

The only proven curative therapy for non-alcoholic fatty liver disease (NAFLD) is improvement in nutrition and increased physical activity targeted to weight loss. In clinical practice, the majority of patients have limited success with making these behavior changes and sustaining them. There is a critical knowledge gap related to the optimal design of lifestyle interventions for NAFLD patients and predictors of response to specific types of treatment interventions. This study aims to evaluate the impact of a mobile technology-based lifestyle intervention program compared to usual care for patients with NAFLD.

2.2 BACKGROUND

NAFLD is a highly prevalent form of chronic liver disease that is caused by fat build-up in the liver. This condition is associated with obesity and underlying metabolic syndrome, and is estimated to affect 25% of adults worldwide. Over time, the fat deposition in the liver can cause inflammation, liver injury and the development of fibrosis (scar tissue) that can progress to cirrhosis and end-stage liver disease. Additional significant associated morbidity and mortality includes development of hepatocellular carcinoma, increased risk of cardiovascular events, and poor health-related quality of life (HRQOL).(1-3) Thankfully, there is a proven curative therapy for NAFLD. A 3-5% reduction in body weight decreases steatosis; a 10% reduction can resolve steatosis, inflammation and fibrosis.(4) Exercise alone, independent of weight loss, has also been shown to reduce steatosis.(5) As a result, lifestyle changes, improved nutrition and physical activity, are first line therapy for NAFLD.(1) Despite the liver and multi-system benefit of this approach and the consequences of untreated NAFLD, the uptake and maintenance of lifestyle interventions is extremely limited in practice. The precise barriers to and reasons for limited uptake of lifestyle changes among individuals with NAFLD are poorly understood. Relatedly, there is an important knowledge gap regarding the optimal design of structured lifestyle programs that would have real-world effectiveness and are low cost, sustainable and scalable tailored to patients with NAFLD. This lack of a standardized approach for lifestyle interventions also has implications for pharmacotherapy trials where variable "placebo effects" stemming from heterogeneous control group implementation of diet and exercise recommendations confound the interpretation of efficacy of these medications.(6)

While highly regimented lifestyle programs have shown to be efficacious, they are often costly, not accessible to many patients, and not amenable to long term sustainability and scalability.(7) Data from the obesity literature indicates that programs that remove logistical barriers (time constraints, cost) and increase the frequency of interactions/ follow-up with real-time feedback have a higher likelihood for real world effectiveness. Mobile technology based lifestyle programs encompass many of these features and have proven to be effective for weight loss among cohorts with similar phenotypes.(8) Preliminary data from our initial pilot trial of a mobile technology-based lifestyle program among NAFLD patients suggest feasibility and efficacy in terms of positive impact on weight loss, physical function, HRQOL and liver and metabolic parameters. Data from a small cohort of NAFLD patients also demonstrated a mobile technology program (text messaging) was effective in promoting weight loss (mean decrease 11-lb compared to none in control group).(9)

In order to assess outcomes of interest, we will employ validated non-invasive biomarkers to assess changes in hepatic steatosis and fibrosis. This includes VCTE, an ultrasound based test that can capture both amount of steatosis via controlled attenuation parameter (CAP) and fibrosis via liver stiffness

measurements. More recently, MRI based imaging tests, MR elastography (MRE) has been shown to have excellent accuracy for assessment of both fibrosis (elastography) and hepatic steatosis (via proton density fat fraction – PDFF). (10) Lifestyle interventions in the general obesity literature and among NAFLD cohorts have been shown to have excellent safety profile with no to minimal adverse events, with primary concern being falls or other musculoskeletal related injuries.

2.3 RISK/BENEFIT ASSESSMENT

2.3.1 KNOWN POTENTIAL RISKS

The risks related to dietary changes and increase in physical activity are minimal, with overall systemic benefit improvements likely far outweighing any potential risks. So long as dietary restriction does not involve > 30% reduction in total caloric intake per day, risks to calorie restriction should be minimal. (11) Regarding physical activity, the overwhelming majority of individuals will be able to partake in a walking program with minimal to no risk. More vigorous exercise will be implemented based on baseline fitness and other factors that may impact potential to achieve higher METS. Potential, but unlikely risks include falls or other musculoskeletal injuries resulting from physical activity, or cardiac events among individuals with cardiac disease who engage in overly ambitious exercise regimens in an unsupervised setting. In terms of survey instruments, these risks are also minimal and rare, but include the potential for feelings of discomfort or anxiety related to answering personal questions. Participants will be able to opt out of answering questions that are discomforting to them. For participants completing MREs, there is a risk of feeling anxious or claustrophobic, transient changes in hearing due to clanging of the machine (rare), and risk related to indwelling metal that can be impacted by the machinery, but this will be addressed with proper screening. Lastly there is a risk of breach of confidentiality and privacy associated with being in the study, including potential breach of the FitBit app.

2.3.2 KNOWN POTENTIAL BENEFITS

Incorporating healthy eating and exercise has been demonstrated to improve HRQOL and multiple systemic metabolic diseases. (12)

2.3.3 ASSESSMENT OF POTENTIAL RISKS AND BENEFITS

The potential risks are minimal as outlined above and are far outweighed by possible benefits.

3 OBJECTIVES AND ENDPOINTS

OBJECTIVES	ENDPOINTS	JUSTIFICATION FOR ENDPOINTS
Primary		
Compare the effectiveness of usual care to a mobile technology based lifestyle intervention on change in liver and metabolic related parameters.	Reduction in amount of hepatic steatosis (≥5% overall reduction in CAP score) at 6 months.	Hepatic steatosis is a liver specific outcome that has been shown to improve with diet and exercise and is associated with risk of downstream clinical outcome such as development of NASH and cirrhosis.
Secondary		

OBJECTIVES	ENDPOINTS	JUSTIFICATION FOR ENDPOINTS
Improvements in other liver-specific and metabolic outcomes	weight loss, increase in total physical activity (based on step counts)	Weight loss has been associated with histologic improvements in NAFLD and NASH. Physical activity has been shown to improve fibrosis, liver enzymes, metabolic parameters and HRQOL.

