1 PROTOCOL SUMMARY

1.1 SYNOPSIS

Title:	A Randomized Controlled Pilot trial of a Structured Mobile Technology Based Lifestyle Program Vs Usual Care for Patients with Non-Alcoholic
	Fatty Liver Disease
Grant Number:	AWD007197
Study Description:	Lifestyle interventions remain first line therapy for the treatment of
Study Description.	non-alcoholic fatty liver disease (NAFLD). In clinical practice, it is challenging for patients to initiate and maintain these changes. In this randomized clinical pilot trial, we will evaluate impact of a structured mobile technology-based lifestyle intervention program compared to usual care to among patients with NAFLD. We hypothesize individuals randomized to the intervention arm will have significantly improved
	outcomes compared to usual care, and that the intervention will be
	feasible, low cost and amenable to large scale implementation.
Objectives:	Primary objective: compare the effectiveness of usual care to a mobile technology based lifestyle intervention on change in liver and metabolic related parameters.
	Secondary objectives: identify predictors associated with reduction in hepatic steatosis and weight loss.
Endpoints:	Primary Endpoint: change in amount of hepatic steatosis
	Secondary Endpoints: change in weight, change in physical activity
Study Population:	120 adult patients with NAFLD including steatosis only, non-alcoholic steatohepatitis (NASH) and NAFLD-related compensated cirrhosis seen in the Michigan Medicine Hepatology clinic.
Phase or Stage:	N/A
Description of Sites/Facilities Enrolling	
Participants:	Michigan Medicine Hepatology Clinics, and patient identified through
i il cicipantor	Data Direct and EMERSE in various local clinics
Description of Study	
Intervention/Experimental	Personalized adaptive lifestyle intervention program that includes
Manipulation:	physical activity and nutritional feedback compared to usual care
Study Duration:	18 months
Participant Duration:	13 months

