4 STUDY DESIGN

4.1 OVERALL DESIGN

This randomized clinical pilot trial will compare a mobile technology-based lifestyle intervention to a waitlist control group receiving usual care for adult patients with NAFLD. The intervention will use FitBit to track and promote physical activity through tailored longitudinal feedback. Patient will also receive nutritional counseling with serial nutritional assessments. The primary endpoint will be change in amount of hepatic steatosis. Secondary outcomes include changes in weight and physical activity (assessed by trend in step counts). A wait-list control design will be applied. 60 Patients will be randomized to the intervention arm for 6 months and 60 to usual care (the wait-list control). Those initially randomized to the intervention arm will then transition to a 6-month post intervention monitoring period to assess maintenance of behavior change and sustainability of impact on outcomes of interest. Individuals initially randomized to usual care, will transition to the intervention at month 6 for a total of 6 months.

The intervention arm will receive tailored physical activity and nutritional counseling, and the waitlist control arm which will follow usual and customary care for NAFLD patients attending our Heptology clinic for 6 months and then receive the 6-month intervention.

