9.3.2 ANALYSIS OF THE PRIMARY ENDPOINT(S)

The primary outcome is change in steatosis. This will be assessed by VCTE controlled attenuation parameter (CAP). A \geq 5% *reduction* in CAP score at 6-months and maintenance at 12 months as this has been associated with clinically meaningful improvements in outcomes.

For individuals with missing data (participants who do not complete follow-up imaging), we will analyze as modified intention to treat and a separate analysis among those who completed all data collection elements.

Subjects will be analyzed according to a modified intention to treat analysis. Individuals who were randomized but never provided FitBit data will not be included in the final analysis

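### The primary endpoint is specified inconsistently (uncut change in steatosis, a CAP fall of at least 5%, or that fall plus 12-month maintenance), and the 5% cut is uncited and costs power if analysed as a responder rate

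*Combined protocol and SAP*

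**What the plan says.** The primary endpoint is described in five places.

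- **Section 1.1, Synopsis:** "Primary Endpoint: change in amount of hepatic steatosis". No measure, cut or time point is given.
- **Section 4.1, Overall Design:** "The primary endpoint will be change in amount of hepatic steatosis". Again there is no cut.
- **Section 3, Objectives and Endpoints:** "Reduction in amount of hepatic steatosis (≥5% overall reduction in CAP score) at 6 months". This adds the measure, the cut and a single time point.
- **Section 9.1, Statistical Hypotheses:** the same 5% CAP cut, stated for participants who complete the intervention, with no comparison to usual care.
- **Section 9.3.2, Analysis of the Primary Endpoint(s):** opens with "The primary outcome is change in steatosis", says it is measured by CAP, and continues with an incomplete sentence on a 5% "reduction* in CAP score at 6-months and maintenance at 12 months as this has been associated with clinically meaningful improvements in outcomes". It names no test and does not say which summary is compared between arms.

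The only stated support for the 5% figure is the clause "as this has been associated with clinically meaningful improvements in outcomes", which carries no reference. Section 2.2 does cite percentage thresholds, but for weight: "A 3-5% reduction in body weight decreases steatosis", with 10% as the level for wider resolution. Section 9.2 ties 80% power at alpha 0.05 to finding parameters associated with a 5% or greater reduction in steatosis and weight loss, not to a comparison of the two arms.

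**The concern.** A comparison of mean CAP change and a comparison of the proportions reaching a 5% fall are different analyses. They can disagree on the same data, and they need different sample sizes. The analysis section is where this should be settled, and it contains both. It also adds a 12-month condition that Section 3 does not have. By month 12 the wait-list arm has received the intervention, so a 12-month element is no longer a comparison with usual care.

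If the cut is the intended analysis, three further matters arise. Its clinical meaning is asserted without a source. A binary cut discards information, which matters with at most 60 patients per arm. And some patients will cross the cut even when the average change is zero, so a response rate without a comparator is hard to interpret. That last point bears on Section 4.2, which names a pre-post analysis of the primary outcome, and on the completer hypothesis in Section 9.1.

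**Working it through.** **1. The plan's own figure.** Section 9.2 gives N = 120, 80% power, alpha 0.05 and dropout of up to 20%. It gives no effect size, SD or response rate, so the figure cannot be reproduced. It can only be inverted. Evaluable per arm = 60 × (1 − 0.20) = 48. For a two-sided two-sample comparison of means, the detectable difference is √(2/n) × (1.960 + 0.842) SD:

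- n = 60: 0.51 SD
- n = 48: 0.57 SD

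For a two-sided comparison of proportions with 48 per arm, 80% power corresponds to about 20% vs 47%, or 30% vs 58%. The plan states none of these.

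**2. Inputs for the comparison of analyses.**

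- From the documents: 60 per arm (Section 4.1), 20% dropout (Section 9.2), two-sided 0.05 (Section 9.3.1), 5% cut (Section 3).
- Assumed, because the documents are silent: baseline CAP 300 dB/m, so the cut is 0.05 × 300 = 15 dB/m; a true between-arm difference of 20 dB/m with zero mean change under usual care; normal changes with a common SD of 20 to 50 dB/m.

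**3. Formulas.** Proportion reaching the cut under usual care: p0 = Φ(−15/SD). Under the intervention: p1 = Φ((−15 + 20)/SD). Continuous power is from the two-sample t-test with effect 20/SD. Responder power is from the two-proportion test with effect h = 2·arcsin√p1 − 2·arcsin√p0. Both use n = 48 per arm.

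| SD (dB/m) | p0 | p1 | Power, continuous | Power, 5% cut |
|---|---|---|---|---|
| 20 | 23% | 60% | 99.8% | 97% |
| 30 | 31% | 57% | 90% | 73% |
| 40 | 35% | 55% | 68% | 49% |
| 50 | 38% | 54% | 49% | 34% |

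At SD 40, 80% power needs 64 per arm for continuous change and 100 per arm for the cut: 100/64 = 1.56 times as many.

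**4. Check on the percent scale.** Set the true difference at 0.57 SD, where continuous change has 80% power with 48 per arm. With an assumed SD of percent change of 5, 8, 10, 15 and 20%, the responder analysis has 52, 58, 59, 60 and 60% power. Regaining 80% takes 94, 80, 78, 77 and 77 per arm against 48, which is 1.6 to 2.0 times as many.

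**5. Crossing the cut with zero mean change.** This is the p0 column: 23% to 38% at SD 20 to 50. At SD 10 it is Φ(−1.5), about 7%. The figure depends on an SD that the documents do not give.

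**6. The cut in absolute terms.** 5% is 12.5 dB/m at a baseline of 250 and 17.5 dB/m at 350, so the required fall varies with baseline.

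**The case against.** The best defence is that the synopsis and Section 4.1 are shorthand for the fuller definition in Section 3. The documents never use the words responder or continuous for this endpoint, and the 5% in Section 3 could be read as a target size of effect. That is fair, and it means the plan does not contain two settled rival endpoints. It does not rescue the plan, because Section 9.3.2 should resolve the ambiguity and instead repeats it.

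A reader might infer three stronger things that the documents do not support.

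- **That the 5% cut has no CAP basis.** Section 9.3.2 does claim one: "this has been associated with clinically meaningful improvements in outcomes". The claim is uncited and unquantified. Whether outside evidence exists cannot be judged from the documents.
- **That a large share of those reaching the cut would be measurement noise.** The SD used above is the total SD of 6-month change, which mixes true change with measurement error. If, as an assumption, half the variance at SD 30 is true change and the mean change is zero, about 85% of those crossing have truly fallen and about 54% have truly fallen by 15 dB/m or more. The documents give no CAP repeatability with which to separate the two.
- **That chance crossing makes a false positive more likely.** In the randomised comparison it affects both arms. It dilutes the contrast and does not raise type I error.

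It is also true that any percentage cut loses information, that this is a pilot, and that at SD 20 the loss is negligible. Pilot status carries limited weight, since the synopsis predicts a significant advantage over usual care and Section 9.2 invokes 80% power.

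**Conclusion.** The point stands as one of specification. The form of the primary endpoint is left open between an uncut change and a 5% cut, its time point is 6 months in Section 3 but 6 months plus 12-month maintenance in Section 9.3.2, and no between-arm summary or test is named. The clinical meaning of the 5% cut is asserted without a source. This rests on the text alone.

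The cost of using the cut is an illustration. Across the assumed SDs of 20 to 50 dB/m, the power loss at 48 per arm runs from about 3 to about 19 percentage points. At an effect where continuous change would have 80% power, the cut needs 1.6 to 2.0 times the patients. That the cut loses power holds at every SD tried; the absolute power figures depend on the assumed baseline, difference and SD. The 23% to 38% crossing rate describes zero mean change under an assumed total SD and is not an estimate of measurement error. It matters most for the uncontrolled readings in Sections 4.2 and 9.1.

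**What to change.** - In Sections 1.1, 3, 4.1, 9.1 and 9.3.2, state one primary endpoint: the between-arm difference in month-6 CAP (dB/m), adjusted for baseline CAP, with the analysis model named in 9.3.2.
- Keep the 5% reduction at 6 months as a supportive summary by arm.
- Make 12-month maintenance a separate secondary analysis.
- Align the power statement in Section 9.2 with the chosen endpoint, giving the assumed difference and SD.
- Cite a CAP-specific source for the statement on clinical meaning, or delete it.

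The cost is wording only. CAP is already scheduled at baseline and month 6 in both arms, so no visits or data are added. The one downside is that the headline becomes a mean difference, which is less immediate to readers than a response percentage; the supportive summary covers that.

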4 STUDY DESIGN

4.1 OVERALL DESIGN

This randomized clinical pilot trial will compare a mobile technology-based lifestyle intervention to a waitlist control group receiving usual care for adult patients with NAFLD. The intervention will use FitBit to track and promote physical activity through tailored longitudinal feedback. Patient will also receive nutritional counseling with serial nutritional assessments. The primary endpoint will be change in amount of hepatic steatosis. Secondary outcomes include changes in weight and physical activity (assessed by trend in step counts). A wait-list control design will be applied. 60 Patients will be randomized to the intervention arm for 6 months and 60 to usual care (the wait-list control). Those initially randomized to the intervention arm will then transition to a 6-month post intervention monitoring period to assess maintenance of behavior change and sustainability of impact on outcomes of interest. Individuals initially randomized to usual care, will transition to the intervention at month 6 for a total of 6 months.

The intervention arm will receive tailored physical activity and nutritional counseling, and the waitlist control arm which will follow usual and customary care for NAFLD patients attending our Heptology clinic for 6 months and then receive the 6-month intervention.

4.2 SCIENTIFIC RATIONALE FOR STUDY DESIGN

This trial will incorporate a wait-list control that will allow us to maximize our ability to assess the primary outcome (by using a pre-post intervention analysis). The 6-month post-intervention follow-up among those initially randomized to the intervention will allow us to assess maintenance of behavior change.

4.3 JUSTIFICATION FOR INTERVENTION

Multiple studies in general obesity research and specifically among patients with NAFLD have shown that patients should aim to achieve ≥150 min/week of moderate intensity physical activity. For diet, the majority of studies have recommended a total caloric reduction of 30% in obese and overweight patients in order to achieve weight loss. We will track total amount of physical activity time and change in nutritional content as part of this intervention.

4.4 END-OF-STUDY DEFINITION

A participant is considered to have completed the study if he or she has completed all phases of the study including the last visit or the last scheduled procedure shown in the Schedule of Activities (SoA), Section 1.3.

The end of the study is defined as completion of the last visit or procedure shown in the SoA in the trial globally.

5 STUDY POPULATION

5.1 INCLUSION CRITERIA

In order to be eligible to participate in this study, an individual must meet all of the following criteria:

- 1. Provision of signed and dated informed consent form
- 2. Stated willingness to comply with all study procedures and availability for the duration of the study
- 3. Age 18 or older
- 4. Diagnosis of NAFLD or NASH based on: liver biopsy (within past 24 months) or imaging [ultrasound (US), vibration controlled transient elastography (VCTE), cat scan (CT), or magnetic resonance imaging (MRI)] within past 24 months
- 5. Ability to communicate in English as their primary language.
- 6. Access to mobile phone/tablet/ or computer compatible with FitBit application and ability to use said device and application.
- 7. Ability to participate in physical activity (reports ability to walk at least several blocks unassisted).

5.2 EXCLUSION CRITERIA

An individual who meets any of the following criteria will be excluded from participation in this study:

- 1. Other causes of liver disease: Alcohol related liver disease (defined as an average 14 or more drinks per week in men and 7 or more drinks per week in women over the past 12 months); viral hepatitis, autoimmune liver disease, hereditary forms of liver disease, etc.
- Medications known to cause hepatic steatosis or other alternative causes of hepatic steatosis: mediations include steroids, tamoxifen, amiodarone, highly active anti-retroviral therapy (HAART), valproate, methotrexate. Other causes of hepatic steatosis include chronic total parenteral nutrition (TPN), severe rapid weight loss.
- 3. Current or prior history of decompensated cirrhosis: variceal bleeding, ascites, hepatic encephalopathy, or hepatocellular carcinoma.
- 4. Inability to make dietary modifications due to significant medical co-morbidity (including but not limited to severe, uncontrolled diabetes).
- 5. Participation in a pharmacologic clinical trial for NAFLD/NASH.
- 6. Plans for invasive procedures or other regimented lifestyle programs for weight reduction (i.e. bariatric surgery, other structured nutrition or exercise program such as University Metabolic Fitness Program, University of Michigan Medical Weight Loss Program, Weight Watchers, etc)
- 7. Current use of weight reduction medications or supplements.
- 8. Active substance abuse or psychiatric disease which limits patient's ability to follow study protocol.
- 9. Recent cardiovascular event (within last 3 months) including myocardial infarction, percutaneous coronary intervention (PCI), coronary artery bypass graft (CABG), cerebrovascular

accident (CVA), transient ischemic attack (TIA), severe cardiac valve disease, complex arrhythmias, class II-IV New York Heart Association (NYHA) heart failure

- 10. Pregnancy based on self-report
- 11. Individuals randomized to MRE cannot have non-MRI compatible metal in their body or severe claustrophobia.

